#### Manifest Refraction

Refraction will be performed by the Investigator or staff using standard clinical practice.

#### ETDRS Testing Methods

##### *Test Set-up*

Best-corrected visual acuity at Baseline and all scheduled follow-up visits will be measured using the ETDRS charts at 1 or 4 meters.

The ETDRS chart must be placed at a distance of 4.00 meters (13 feet and 1.5 inches, or 157.5 inches) from cornea to chart surface, when using a 4-meter chart. For testing at 1 meter, the distance must be 1.00 (39 and 3/8 inches). A measuring tape or meter stick should always be available to verify the chart distance, even if the examining chair is supposed to be immovable or if reference marks are placed on the floor or walls.

The 1-meter distance is measured from the eye of the participant, seated comfortably in a chair with his/her back firmly placed against the chair, to the center of the 2nd or 4th letter of the 3rd line of the chart.

**Note:** If it is necessary to refract at the 1-meter distance, remember to add +0.75 sphere to the trial frame. Subtract the +0.75 sphere from the final refraction obtained at the 1-meter distance before recording the refraction on the form.

*Methods*

Starting at 4 meters, the subject should attempt to read each letter, line-by-line, left to right, beginning with line 1 at the top of the chart. If the subject is unable to read line 1 (20/200) at 4 meters, then visual acuity testing should be performed at 1 meter.

The subjects should be told that the chart has letters only, no numbers. If the subject reads a number, he or she should be reminded that the chart contains no numbers, and the examiner should then request a letter in lieu of the number. The subject should be asked to read slowly, about one letter per second, so as to achieve the best identification of each letter. He/she is not to proceed to the next letter until he/she has given a definite response.

A maximum effort should be made to identify each letter on the chart. When the subject says he/she cannot read a letter, the subject should be encouraged to guess. If the subject identified two (2) letters (e.g., A or B), the subject should be asked to choose one letter and, if necessary, to guess. When it becomes evident that no further meaningful readings can be made despite encouragement to read or guess, the examiner should stop the testing for that eye. However, all letters on the last line should be attempted as letter difficulties vary and the last letter may be the only one read correctly. The number of letters missed or read incorrectly should be noted.

In order to provide standardized and well-controlled assessment of visual acuity, all visual acuity assessments for a subject should be performed consistently (e.g., the same lighting conditions, viewing distance, etc.) at each visit.

*Recording and Scoring Best-Corrected Visual Acuity*

Using the Visual Acuity Worksheet, circle each letter the subject identifies correctly, write total correct for each row in the place provided, and compute the total correct for all rows. Do not mark letters read incorrectly or not read at all. Each letter read correctly is recorded as one. Only move to the next line if 4 or more letters are read correctly. If 3 or more letters are read correctly in the final line, then that line is used for the Snellen equivalent and the visual acuity score. If 2 or fewer letters are read correctly in the final line, letters read from that line are added to the total visual acuity score and the previous line is used for the Snellen equivalent.

The number of correct letters will be recorded on the study worksheets and entered into the EDC. For the Day 1 Visual Acuity measurement, if two measurements are made,

one BSCVA and one with manifest refraction, the latter VA obtained with manifest refraction should be entered into the EDC.

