## 8 STUDY SELECTION CRITERIA

### 8.1 INCLUSION CRITERIA

For inclusion in this study, subjects must meet all of the following criteria:

1. At least 22 years of age
2. Reports dry eye symptoms within the past 3 to 6 months
3. Reports having to use artificial tears or lubricants regularly over the past month to relieve dry eye symptoms.
4. Schirmer tear test (with anesthesia)  $\geq 5$  to  $\leq 15$  mm in 5 minutes
5. OSDI Score of 23-79
6. TBUT of  $\geq 1$  to  $\leq 7$  seconds in both eyes
7. Meibomian gland obstruction in both eyes based on a total Meibomian Gland Secretion Score  $\leq 12$  in each eye.
8. At least 15 glands in each lower eyelid should be expressible, with a sterile cotton swab, at the slit lamp.
9. Best corrected visual acuity of 20/100 or better in both eyes.
10. Willing and able to comply with the study procedures and follow-up
11. Willing and able to provide informed consent
12. English-speaking

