### **12.6.3 SECONDARY SAFETY ENDPOINTS**

The secondary safety endpoints include:

- Change in best corrected visual acuity (ETDRS)
- Change in intraocular pressure (IOP)

These endpoints will be summarized by treatment group and visit.

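### Section 21.2 moves an eye that cannot read 20/200 at 4 m to 1 m but enters raw letter counts with no distance conversion, understating acuity loss by about 30 letters and conflicting with its own same-distance instruction

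*Combined protocol and SAP*

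**What the plan says.** The acuity method is in Appendix A, section 21.2. Under Test Set-up, acuity "will be measured using the ETDRS charts at 1 or 4 meters". Under Methods, testing begins at 4 m from the top line, and then: "If the subject is unable to read line 1 (20/200) at 4 meters, then visual acuity testing should be performed at 1 meter".

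The scoring rules follow under Recording and Scoring Best-Corrected Visual Acuity: "Each letter read correctly is recorded as one", the rows are totalled, and "The number of correct letters will be recorded on the study worksheets and entered into the EDC". The only adjustment for the shorter distance concerns the lens: "If it is necessary to refract at the 1-meter distance, remember to add +0.75 sphere to the trial frame". That corrects refraction, not the score. Just before the scoring rules, the section also asks that each subject be tested under the same conditions at every visit, and it names viewing distance as one of them.

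The letter score is used in three places:

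- Change in BCVA is a secondary safety endpoint (sections 6.2 and 12.6.3), summarised descriptively.
- A loss of 10 or more letters is on the list of anticipated ocular adverse events (section 10.2).
- Worsening by 10 or more letters at Day 1 or Week 1 calls for manifest refraction and a repeat measurement (section 21.2 and the footnotes to Tables 3 and 4).

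Eligibility in section 8.1 requires "Best corrected visual acuity of 20/100 or better in both eyes".

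**The concern.** Every eligible eye can read the 20/200 line at baseline, so every baseline count is taken at 4 m. Only an eye that has worsened past 20/200 moves to 1 m, where the same printed letters subtend four times the angle. Subtracting a 4 m count from a 1 m count mixes two scales. The error runs in one direction, towards a smaller loss or an apparent gain, and it falls only on eyes with severe loss.

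At stake are the accuracy of the BCVA change summary at every visit and the reliability of the 10-letter criterion in the eyes where it matters most. Visual loss is not remote for this device: section 5.2.4 reports device-related loss of acuity in two TearCare subjects of the preceding trial, although nothing there suggests that either eye fell below 20/200.

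**Working it through.** **Inputs from the documents.** Distances of 4 m and 1 m; line 1 is 20/200 at 4 m; one point per correct letter; raw count entered (all section 21.2). Worst eligible baseline is 20/100 (section 8.1). The threshold is 10 letters (sections 10.2 and 21.2, Tables 3 and 4).

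**Assumptions not in the documents.** (a) The same chart is used at both distances. (b) Each line has 5 letters and a step of 0.1 logMAR. Assumption (b) is needed only for letter counts.

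**The plan's own geometry.** The plan gives no letter conversion to reproduce, but its distance figures are consistent:

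- Lens add: 1/1 − 1/4 = 0.75 D, as stated.
- 4 m: 4/0.0254 = 157.48 in, against 157.5 stated.
- 1 m: 1/0.0254 = 39.37 in, against 39 3/8 stated.

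**Size of the offset.** A line that is 20/X at 4 m is 20/(4X) at 1 m. In letters, 5 × log10(4)/0.1 = 5 × 0.602/0.1 = 30.1. So

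true change ≈ (letters at 1 m − letters at 4 m) − 30.

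**Worked case.** At 4 m the lines run 20/200, 20/160, 20/125, 20/100, so 20/100 is line 4, or 20 letters. At 1 m that same line is 20/400, again 20 letters. Recorded change = 20 − 20 = 0; true change ≈ −30. Given assumption (a), the zero follows from the 4:1 ratio alone, because the same printed line is read.

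**Recorded change when the eye is moved to 1 m** (whole lines; subtract 30 for the true change):

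| Baseline (letters at 4 m) | 20/250 (30 at 1 m) | 20/320 (25) | 20/400 (20) | 20/500 (15) | 20/640 (10) | 20/800 (5) |
|---|---|---|---|---|---|---|
| 20/100 (20) | +10 | +5 | 0 | −5 | −10 | −15 |
| 20/80 (25) | +5 | 0 | −5 | −10 | −15 | −20 |
| 20/63 (30) | 0 | −5 | −10 | −15 | −20 | −25 |
| 20/50 (35) | −5 | −10 | −15 | −20 | −25 | −30 |
| 20/40 (40) | −10 | −15 | −20 | −25 | −30 | −35 |

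The 10-letter criterion is missed wherever the recorded change is above −10:

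- from 20/100, falls to 20/250 through 20/500;
- from 20/80, falls to 20/250 through 20/400;
- from 20/63, falls to 20/250 and 20/320;
- from 20/50, a fall to 20/250 only.

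From 20/40 or better every switch still records a loss of at least 10 letters, but 30 too few.

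**The other instruction.** If viewing distance is held constant, the 20/100 eye that falls to 20/400 stays at 4 m and reads nothing: 0 − 20 = −20. The criterion fires. The same eye therefore records either 0 or −20, depending on which sentence the site follows.

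**The case against.** The strongest objection is the same-distance sentence. A reader might infer from the switch rule that a fall from 20/100 to 20/400 is bound to be recorded as no change. The documents do not support that certainty, because the constant-distance instruction would give a 20-letter loss. This stands. The switch rule is the more specific text and is written for exactly these eyes, but the defect is a conflict plus a missing conversion, not a guaranteed zero.

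Second, the wording could allow a separate chart designed for 1 m, in which case the 30-letter offset need not apply. This stands as an assumption. The same-chart reading is the more natural one: moving closer helps a subject who failed 20/200 only if the letters become larger in angle.

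Third, the acuity worksheet is not in the documents and might carry a distance field or a conversion. This has little force, because the text says that the number of correct letters is what is recorded and entered. A Snellen equivalent is also derived, but nothing adjusts it for 1 m, and the criteria are in letters.

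Fourth, a reader might infer that sight-threatening loss would go undetected. That does not follow. Ocular adverse events must be documented whatever the letter difference (section 10), and the investigator is responsible for identifying them (section 10.3). A sight-threatening event is serious and reportable in its own right (section 10.1), and a slit lamp exam is scheduled at every visit with an acuity test. The examiner also sees the failure at 4 m, since the chart distance has to change. What is distorted is the recorded score and the rules computed from it.

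**Conclusion.** The point holds in a limited form. As written, the switch rule combined with raw-count entry gives a wrong BCVA change, too favourable by about 30 letters, for any eye moved from 4 m to 1 m. It also contradicts the constant-distance instruction in the same section. The 30-letter figure rests on the same chart being used at both distances and on a standard layout of 5 letters per 0.1 logMAR line.

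A reader might take this to disable the 10-letter criterion for all severe losses. It does not: the criterion is missed only for baselines of about 20/50 to 20/100 falling into the band tabulated above. Elsewhere the loss is understated but still flagged. The repeat-refraction trigger applies only at Day 1 and Week 1, whereas the understated change can affect any visit with an acuity test.

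The documents give no basis for an expected count, but few eyes should be affected. The endpoint is secondary and descriptive, and no effectiveness endpoint, power figure or success criterion depends on it. It merits correction because the error favours apparent safety in the worst-affected eyes and costs little to remove.

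**What to change.** In section 21.2, reconcile the switch to 1 m with the instruction to keep viewing distance constant, and state whether the same chart is used at both distances. Add test distance to the acuity worksheet and the EDC. Define one distance-adjusted letter score, or logMAR, with the offset confirmed against the chart in use (30 letters under the layout assumed here). Use that score for change from baseline in section 12.6.3 and for the existing 10-letter criteria in sections 10.2 and 21.2 and the Table 3 and Table 4 footnotes. The criteria themselves need not change.

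The cost is one data field, one derivation rule and a short clarification to sites, with no additional testing. For visits already completed, distance can be back-filled only where the source worksheet shows it; any eye for which it cannot be established should be listed.

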### 21.3 SLIT LAMP EXAM

**Masked assessment:** This assessment should be performed by the masked assessor.

A standard slit-lamp examination shall be performed including inspection of the cornea at a magnification of 10X and/or 16X for the presence or active inflammation or structural change, the iris and anterior chamber for inflammation, and the eyelids for crusts, collarettes, or scales.

### 21.4 TEAR BREAKUP TIME (TBUT)

**Masked assessment:** This assessment should be performed by the masked assessor.

Tear film stability is measured by a test of TBUT, defined as the time to initial breakup of the tear film after a blink.

#### Measuring Tear Break-Up Time

1. The fluorescein-impregnated strip is moistened with sterile saline and applied gently by touching against the superior bulbar conjunctiva.
2. Measure TBUT approximately 30 seconds after instilling the fluorescein. Ask the subject to blink several times and to move the eyes, to mix the fluorescein in the tears.
3. Use the cobalt blue illumination of the slit lamp and a Wratten filter. Use a beam width of approximately 4 mm, and full height. Move the beam slowly from side to side to cover the entire cornea.
4. Ask the subject to blink 3 times and then hold their eye open (e.g., “Blink, blink, blink, hold”).
5. Using a stopwatch, record the time when the tear film breaks-up. The time from upstroke of the last blink to the first tear film break or dry spot formation is recorded as the TBUT measurement.
6. Repeat the test 3 times per eye and take the average of the 3 measurements.

 DEWS. The definition and classification of dry eye disease: report of the Definition and Classification Subcommittee of the International Dry Eye WorkShop. *Ocul Surf.* 2007;5:133.

 Norn MS. Desiccation of the precorneal tear film. I. Corneal wetting time. *Acta Ophthalmol (Copenh)* 1969;47:865–880.

#### **Tips for Tear Break-up Time**

- TBUT is the number of seconds between a blink and the appearance of a first dry spot or negative staining in the tear film.
- TBUT measurements should be done quickly after installation of the dye because, in the presence of epithelial defects, the fluorescein will diffuse into the tissue and the borders of staining become indistinct, as does the intensity of staining of both tear film and cornea.
- Clear instructions should be provided to subjects about the blink and hold sequence
- Clear instructions should be provided to the study staff about when to start the stopwatch

## **21.5 CORNEAL STAINING**

**Masked assessment:** This assessment should be performed by the masked assessor.

#### **Measuring Corneal staining**

[figure not shown]
1. Measure corneal staining within 3-4 minutes of installation of fluorescein dye to assure the dye does not diffuse into stroma, blurring the discrete margin of any staining defects.
2. Use moderate illumination on the slit-lamp and use cobalt blue filter on with yellow Wratten filter to improve any visualization of corneal staining. Use 3 mm width and 10x magnification for assessing corneal staining.
3. Grade the corneal staining using the NEI/Industry Grading System provided in Figure 7 below.

---

 Lemp MA. Report of the National Eye Institute/Industry workshop on Clinical Trials in Dry Eyes. CLAO J 1995;21: 221–232.

**Figure 7: NEI/Industry Grading System for Corneal Staining**

Score each of 5 areas of the cornea and total score:

### Grade 0: No staining

#### Grade 1: Scattered, micropunctate staining

### Grade 2: Grouped, micropunctate staining

### Grade 3: Diffuse micropunctate or macropunctate staining

## Tips for Corneal Staining

- Ask subjects to blink several times to assure the uniform distribution of dye in cul-de-sac
- Make sure to use moderate illumination to avoid hyper reflection from the spots of fluorescein uptake

[figure not shown]
## 21.6 CONJUNCTIVAL STAINING

**Masked assessment:** This assessment should be performed by the masked assessor.

1. The lissamine green-impregnated strip is moistened with sterile saline and applied gently by touching against the superior bulbar conjunctiva.
2. Wait at least 1 minute before grading the conjunctival staining. Perform grading within 4 minutes of instilling the dye.
3. Start with a low illumination and increase the level until the lissamine green staining is most visible.
4. Grade the conjunctival staining on moderate illumination per the NEI grading system shown below in Figure 8.

**Figure 8: NEI/Industry Grading System for Conjunctival Staining**

Score each of 6 areas of the conjunctiva and total score:

Grade 0: No staining

Grade 1: Scattered, micropunctate staining

Grade 2: Grouped, micropunctate staining

Grade 3: Diffuse micropunctate or macropunctate staining

#### Tips for Conjunctival Staining

- Ask subjects to blink several times to assure the uniform distribution of dye in cul-de-sac
- Make sure to identify pooling or a stained mucus strand. Ask subjects to blink a couple of times when in doubt.

## 21.7 SCHIRMER TEST

The Schirmer Test measures aqueous tear quantity and is an indication of aqueous-deficient dry eye.

#### Procedure

- The Schirmer test, with anesthesia, should be performed in a dimly lit room.
- Instill 1 drop of anesthetic into each eye and wait approximately 4 minutes.
- Gentle blotting of the corners of the eyelids with a facial tissue is allowed to catch the over spill. Any direct, active blotting of the cul-de-sac will not be allowed.
- Ask the patient to look up and draw the lower lid gently downward and temporally hook the rounded bent end of the sterile strip into the lower cul-de-sac at the temporal one-third of the lower eyelid margin.
- Start the timer
- To minimize artifacts from this test, ask subjects to gently close their eyelids until 5 minutes have elapsed. Ask subjects to open their eyes and remove the strips.
- Because the tear front will continue advancing a few millimeters after it has been removed from the eyes, it is important to mark the tear front with a ball point pen at precisely 5 minutes.

**Strip Measuring**

1. Write the letter “R” on the strip used in the right (OD) eye and the letter “L” on the strip used in the left (OS) eye. Each strip has graduated sections on it that will aid in capturing the appropriate measurement in millimeters.
2. Record only whole numbers, rounding up to the nearest whole number if the tear front is at or greater than the half-millimeter mark.
3. Once marked, each strip will be affixed to the source document (marked side up), in the space provided, and covered completely with transparent tape. The measurement is then to be captured on the source document and transcribed onto the EDC.

## **21.8 MEIBOMIAN GLAND SECRETION SCORING**

**Masked assessment:** This assessment should be performed by the masked assessor.

The Meibomian Gland Secretion Scoring is an assessment of the quality of the secretions produced by the meibomian glands in the lower eyelids. The Meibomian Gland Secretion Scoring should be performed using the Meibomian Gland Evaluator (TearScience, Inc.). Ensure that the instrument has been cleaned using alcohol prior to each use.

Grade the quality of secretions in the lateral, central and temporal thirds of the lower eyelids. Grade the 5 central glands in each region, for a total of 15 glands per eye.

Per the method described by Korb et al, place the part of the instrument's contact surface onto the skin immediately inferior to the eyelashes of the lower eyelid so that the long dimension is parallel to the eyelid margin. Once full contact is achieved between the instrument and the skin immediately below the lash line of the lower lid, rotate the shaft of the instrument downward approximately 15 to 45 degrees. Then, depress the shaft midway (~3mm) and roll the lower eyelid margin slightly outward. Make sure to avoid contact with the ocular surface.

Hold the instrument in place over each third of the lid for a minimum of 10 and a maximum of 15 seconds while grading the quality of secretion of the 5 glands in the center of the instrument (15 glands total per eye). Grade the quality of the secretions per the following scale described by Lane et al:

---

- 0 = nothing
- 1 = toothpaste
- 2 = cloudy
- 3 = clear

From this assessment the following endpoints will be calculated:

- Total Meibomian Gland Secretion Score: Sum of the grade (0 – 3) for each of the 15 glands. Range for this score is 0-45.
- Count of the number of Meibomian glands yielding clear liquid secretions. Range for this count is 0-15.
- Count of the number of glands secreting any liquid (clear or cloudy). Range for this count is 0-15.

## 21.9 INTRAOCULAR PRESSURE

**Masked assessment:** This assessment should be performed by the masked assessor.

The same method of measuring intraocular pressure should be used at each visit. Intraocular pressure should be measured with applanation tonometry (e.g. Goldmann tonometer, if available).

## 21.10 BLINK RATE

**Masked assessment:** This assessment should be performed by the masked assessor.

The blink rate of each subject will be measured over a three-minute period using a computer-based algorithm customized to count blinks per minute. Subjects will be instructed to look at a stimulus displayed on computer screen (while seated) and eyelid closure incidences will be collected. Make sure to record the start and stop time of when subject starts and stops viewing the stimulus displayed on the computer screen. Lighting that may cause squinting or minimizes the interpalpebral fissure will be directed away from a subject's field of vision and the monitor brightness will be adjusted to a level which would not cause squinting or minimizes the interpalpebral fissure. Sites will be instructed with the specifications about the brightness, contrast, resolution and ambient light parameters while conducting the test. Blink rate will be utilized to calculate the inter-blink-interval (IBI) and ocular protection index (OPI).

## **21.11 QUESTIONNAIRES**

### **21.11.1 GENERAL INSTRUCTIONS FOR QUESTIONNAIRES**

The subject should complete all required questionnaires at the beginning of each visit before conducting other clinical testing.

Provide a paper copy of the questionnaires and a blue or black ink pen to the subject. Review the instructions for each questionnaire with the subject and answer any questions they have about how to complete them. Then allow the subject to complete the questionnaires on their own (i.e., self-administered) without any assistance.

Study staff should review the questionnaires before the subject leaves the office to check for missing or multiple answers on a given question. If these are found, please point this out to the subject and allow them to revise their response(s) to the specific question(s). Please confirm initials and date of the subject on the last page of the questionnaire. Do not allow the subject to take the questionnaires home.

